knowledge, risk perception, and participation. Furthermore it helped them clarify their values and preferences, and prepare them for the encounter with their physician and deciding on a course of action.¹⁴ In addition, patients who used decision aids were less anxious and more likely to prefer nonoperative treatment, while outcomes were unaffected.³ Most often a decision aid addresses treatment opportunities and tailors questions to clarify patients' wishes, as recommended by the Ottawa Decision Support Framework.¹⁴

Although the literature is clear about the advantages of decision aids in the process of decision-making, studies are inconclusive about the effect of decision aids on patient satisfaction.¹⁵ Of the 86 RCT's identified by Stacey et al., eleven studies measured satisfaction.³ Of these, four studies reported that people exposed to decision aids had higher satisfaction with their choice compared to usual care, and the remaining seven reported no statistically significant difference.¹⁶

Studies that have directly investigated the effect of decision aids in orthopaedic practice are limited and further study is necessary to determine the best way to implement decision aids in a clinical orthopedic practice.⁵⁷⁻¹² Randomized trials evaluating the impact of decision aids on patient knowledge, decisional conflict, satisfaction, and outcomes may have substantial impact in hand surgery where most treatments are elective and address quality of life.

II. SPECIFIC AIMS (Research Objectives)

Primary Study Question:

The objective is to apply decision aids, which are based on the Ottawa Framework and International Patient Decision Aids Standards (IPDAS) criteria, to two randomly selected patient cohorts (Cohort I and Cohort II) for each diagnosis. The diagnoses will include patients with trapeziometacarpal (TMC) arthrosis, carpal tunnel syndrome (CTS), cubital tunnel syndrome (CTD), distal radius fractures (DRF) and trigger finger (TF). Cohort I is comprised of patients managed with a decision aid, and Cohort II is comprised of patients managed without a decision aid. This distinction is made to evaluate whether the use of a decision aid results in different scores on variables reflective of the decision-making process, behavior, health outcomes, communication, and healthcare system.

Primary Null Hypothesis:

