We plan a prospective randomized controlled study with a null hypothesis that patients randomized to a newly developed decision aid in addition to usual care have no difference in decisional conflict compared to patients treated with usual care and the ASSH brochures.

Secondary Null Hypotheses:

Our second aim is to determine if decision aids influence patient satisfaction, clinical outcomes and regret. To address this second aim, we will test the null hypothesis, which is that there is no difference in the rate of satisfaction, clinical outcomes and regret between patients treated with and without a decision aid.

III. SUBJECT SELECTION

Participants will be recruited among patients presenting to Orthopedic Hand Service of Massachusetts General Hospital with moderate or severe TMC arthrosis or CTS or CTD or DRF and or TF. The study physician will confirm the diagnosis and introduce the study to the patient. Each participant following the explanations by the interventionist will sign a detailed consent form at the time of their baseline diagnostic assessment. The consent form will include all of the study procedures, information about potential risks and benefits of participation, and information regarding who they can contact for further questions. It also will state that participation is voluntary, that participants can refuse to answer any question, and that they can withdraw from the study at any time, and that study participation is in no way related to their care. For follow-up, participants may be contacted by mail, phone and email.

Inclusion criteria:

All adult (>18years old) English-speaking patients presenting to one of the participating hand surgeons, [name], [name], [name] and [name] from the Massachusetts General Hospital with moderate or severe TMC arthrosis, CTS, CTD, DRF and TF will be invited to enroll.

Exclusion criteria include:

1. Patients with prior operative treatment or corticosteroid injection for TMC, CTS, CTD, DRF and TF on the same limb.
2. Patients that have previously used the Decision Aids

IV. SUBJECT ENROLLMENT

The study will be described in detail and the treating physician/study staff will obtain informed consent. Patients will be given a copy of the consent form and be informed that their participation is voluntary and that they may refuse at anytime. The enrolling physician will emphasize that participation is voluntary.

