All patients will be randomized to either a cohort managed with a decision aid (Cohort I) or to a cohort managed without a decision aid (Cohort II). A research fellow does the randomization after the first consult at the outpatient clinic with a computer generated simple randomization sequence.

V. STUDY PROCEDURES

This study will employ a randomized, prospective design. The baseline data are gathered at enrollment. The patients will be randomly assigned to two different cohorts after the encounter with the physician. The physician will be informed that the patient is participating in this study, but will not know to which cohort the patient will be randomized.

Cohort I will be managed with standard care plus a decision aid (henceforth “DA”), and cohort II will be managed without one. The patients in Cohort I will receive the DA, which they can complete in a separate room and take home. The decision aids include information on the disease/condition, treatment options, benefits, risks, scientific uncertainties, and probabilities of potential outcomes tailored to the patient’s health risks factors. Additionally, it includes values clarifications such as describing outcomes in functional terms, asking patients to consider which benefits and risks matter most to them, and guidance in the steps of decision making and

discussing their decision with family/friends. It is interactive and dynamic, helping patients clarify their preferences and come to a decision that feels best to them.

Cohort II will receive the standard care including—at the surgeon’s discretion—the American Society of Surgery of the Hand (ASSH) informational brochure. The patients will have the opportunity to read the brochure in a separate, quiet room or take it home. The ASSH - brochure contains anatomic illustrations of the injury and a discussion of surgical and non-surgical treatments for the diseases, and a general description of expected outcomes. Similar to the patients in cohort II, the patients in cohort I can read and complete the DA in a separate quiet room and take the decision aid home.

After randomization all patients will complete the REDCap questionnaires about the conflict in decision-making, which will take approximately 20 minutes. After completing the study procedures, the physician will return to the room and continue with the visit with the patient. The visit will be timed by a member of the study staff.

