Outcome: Measured variables at enrollment – with REDCap, which will take approximately 20 minutes to fill out:

Demographic Questionnaire:

- Age
- Sex
- Ethnicity
- Race
- Marital status
- Education
- Current work status
- Current or previous occupation
- Hand dominance

Primary outcome:

- Decision conflict scale (DCS) – quantifies the state of uncertainty about a course of action.
- 11-point ordinal satisfaction scale – quantifies the satisfaction with overall treatment.
- 11-point ordinal satisfaction scale – quantifies the satisfaction with decision-making.

Secondary outcome

- Knowledge questionnaire
- Stage of decision making
- Decision Self-efficacy Scale
- Acceptability (Cohort 1 will not receive this questionnaire)
- Pain Self efficacy Questionnaire (PSEQ)
- 9-item Shared Decision Making Questionnaire (SDM-Q-9)

Primary health outcomes variables:

- Quick-DASH
- EQ-5D

At follow-up 1 week-1 month and 6 months after enrollment we will have patients complete the following online REDCap questionnaires, which will take approximately 20 minutes:

The decision-making process variables:

- Quick-DASH
- PROMIS Upper Extremity CAT
- DCS
- 11-point ordinal satisfaction scale – quantifies the satisfaction with overall treatment and decision-making.

- 11-point ordinal satisfaction scale – quantifies the satisfaction with decision-making.
- Decision Regret scale (measures distress or remorse after a health care decision)

VI. BIOSTATISTICAL ANALYSIS

Statistical issues

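### Acceptability is a listed secondary outcome, but the plan withholds the form from Cohort 1, the decision-aid arm, so as written no decision-aid user rates it

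*Combined protocol and SAP*

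**What the plan says.** The list of variables measured at enrollment (Section V, Study Procedures) has a secondary-outcome block of six instruments. The fourth reads "Acceptability (Cohort 1 will not receive this questionnaire". None of the other five is limited to one cohort.

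The cohorts are defined in three places:

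- Section II, Specific Aims: "Cohort I is comprised of patients managed with a decision aid, and Cohort II is comprised of patients managed without a decision aid".
- Section IV, Subject Enrollment, which describes randomization to "a cohort managed with a decision aid (Cohort I") or to a cohort without one.
- Section V, Study Procedures: "Cohort I will be managed with standard care plus a decision aid".

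The later questionnaires are introduced in Section V with "At follow-up 1 week-1 month and 6 months after enrollment we will have patients complete the following online REDCap questionnaires". The list that follows does not include Acceptability, and the form is mentioned nowhere else in the document.

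**The concern.** Acceptability is naturally a question for people who have used the thing being rated. The intervention under test is new; the primary null hypothesis is that "patients randomized to a newly developed decision aid in addition to usual care have no difference in decisional conflict". A reader would expect an acceptability outcome in such a trial to come from the patients given the aid. The note assigns it to the other arm.

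The note is also an operational instruction. The questionnaires are delivered through REDCap, and Section IX says that REDCap supports skip patterns. A build that follows the text would suppress the form for every Cohort I patient. The loss could not be repaired in analysis. With no Cohort I values there is nothing to compare, and the mean imputation allowed in Section VI could only carry control-arm ratings into the decision-aid arm.

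**Working it through.** The question is one of consistency between sections, so the check is mainly a reading of the text.

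**1. Which arm is Cohort 1?** The note uses an Arabic numeral and the rest of the protocol uses Roman numerals. Only two cohorts exist, I and II, and no other numbering is defined. Cohort I is the decision-aid arm in all three definitions (Sections II, IV and V), and no passage reverses them. Cohort 1 in the note therefore means the decision-aid arm.

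**2. What is collected at enrollment?** The secondary instruments are Knowledge, Stage of decision making, Decision Self-efficacy, Acceptability, PSEQ and SDM-Q-9, which makes 6. One of the 6 is restricted by cohort. By that rule, Acceptability forms from Cohort I at enrollment = 0.

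**3. Is it collected later?** The follow-up list has Quick-DASH, PROMIS Upper Extremity CAT, DCS, two satisfaction items and Decision Regret, which makes 6. Acceptability is not among them. Neither are the other five secondary instruments, so its absence follows the general pattern for these measures. Acceptability forms from Cohort I at follow-up = 0.

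**4. Could Cohort II contain users of the aid?** By design it does not receive the aid, and Section III excludes patients who have used the decision aids before. On the plan as written, the forms from Cohort II do not come from users.

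**5. Total.** Ratings by decision-aid users = 0 (enrollment) + 0 (follow-up) = 0.

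**6. Scale.** Section VI gives 126 patients in total for 80% power, an effect size of 0.5 and an alpha of 0.05. With a two-sided test and the normal approximation, n per arm = 2 × (1.960 + 0.842)² / 0.5² = 62.8, rounded up to 63, and 2 × 63 = 126, which reproduces the stated figure. The allocation ratio is not stated. Under an assumed 1:1 allocation, about 63 patients would use the aid and none would rate it, while about 63 in Cohort II would receive the form. The zero does not depend on these numbers.

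**7. What depends on it?** The null hypotheses name four outcomes: decisional conflict, satisfaction, clinical outcomes and regret. Acceptability is none of them. Section VI names no specific analysis of it. Of the general methods there, between-group tests could not be applied to it, and only a description of the control arm would be possible.

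**The case against.** The strongest reply is that this is a clerical slip in one parenthesis about an outcome that appears in no aim, hypothesis, sample-size calculation or named analysis. That is fair as to its weight, and it is why the consequence is put no higher than one secondary instrument. It does not remove the point, because the parenthesis decides who receives the form.

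A second reply is that the form may be meant for control patients only, as a rating of the brochure or of usual care. This stands in part. The documents do not say what the form rates, so the reading cannot be excluded, and a reader who concludes that the label is certainly reversed goes further than the text allows. But if this was the intention the protocol does not say so, and the outcome would still say nothing about the acceptability of the decision aid.

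A reader might also treat the absence from follow-up as a second defect. It is not one. All six secondary instruments are enrollment-only, and the follow-up list matters here only because it shows that no later collection makes up for the restriction.

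Finally, the REDCap build is not shown, so whether the form is in fact suppressed is unknown. The finding concerns the plan as written.

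**Conclusion.** The point holds. As written, no decision-aid user rates acceptability at any time, and a listed secondary outcome yields control-arm data only. It can neither describe the new aid from its users' side nor support a comparison between arms, at any sample size.

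The size is limited: 1 of 6 secondary instruments is affected, and 0 of the 4 outcomes named in the null hypotheses. It would be wrong to infer that the primary comparison on decisional conflict, or the comparisons of satisfaction, clinical outcomes or regret, are weakened, since none of them uses this form.

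Two assumptions are involved. Cohort 1 is read as Cohort I, which is secure because no other numbering exists. A reversed label is taken as the probable cause, which is plausible but not confirmed. The conclusion rests on the first only. The second affects which correction is right, and the sponsor has to settle it.

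**What to change.** State in Section V what the Acceptability form rates, which cohort or cohorts receive it and when. Then correct the note and the REDCap branching to match:

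- If the form rates the decision aid, the note should name Cohort II, not Cohort 1, as the cohort that does not receive it.
- If it rates information material in general, remove the restriction and give it to both cohorts.
- If a control-only rating of the brochure or of usual care was truly intended, say so, and do not present the outcome as acceptability of the decision aid or as a between-arm comparison.

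Under either of the first two options the cost is one corrected note, one branching rule and one additional form for Cohort I within the enrollment battery, which the protocol puts at about 20 minutes. The length of the form is not given, so the added burden cannot be stated. The third option costs only a clarifying sentence. Sample size and the primary outcome do not change under any of them.

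### EQ-5D is labelled a primary health outcome but is scheduled only at enrollment, so it cannot show an effect of the decision aid that runs through treatment

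*Combined protocol and SAP*

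**What the plan says.** Section V (Study Procedures) sets out two instrument lists.

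The first is introduced by "Outcome: Measured variables at enrollment – with REDCap, which will take approximately 20 minutes to fill out". Within it, the sub-heading "Primary health outcomes variables" covers Quick-DASH and EQ-5D and nothing else.

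The second begins "At follow-up 1 week-1 month and 6 months after enrollment we will have patients complete the following online REDCap questionnaires". It names Quick-DASH, "PROMIS Upper Extremity CAT", the Decision Conflict Scale, the satisfaction scales and the Decision Regret scale. EQ-5D is not among them, and it is mentioned nowhere else in the protocol.

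On timing, Section V states that "The baseline data are gathered at enrollment". It also says that "After randomization all patients will complete the REDCap questionnaires about the conflict in decision-making", and then that "After completing the study procedures, the physician will return to the room and continue with the visit with the patient".

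The aim that these instruments serve is under Secondary Null Hypotheses in Section II: "there is no difference in the rate of satisfaction, clinical outcomes and regret between patients treated with and without a decision aid". Section VI (Biostatistical Analysis) plans independent t-tests, paired t-tests within a group across occasions, and descriptive summaries at every time point.

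**The concern.** An outcome has to be measured at a time when the intervention could have changed it. A decision aid can alter clinical outcome mainly by altering which treatment is chosen and how the patient follows it through, and that takes time. An instrument called a primary health outcome but answered only at the enrollment visit cannot show such a change.

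EQ-5D is the only generic health-status measure in the plan. The background in Section I justifies the trial partly on the ground that most hand-surgery treatments are elective and concern quality of life. As scheduled, generic health status is missing at every point where treatment could have affected it, and readings not taken at 6 months cannot be recovered later.

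**Working it through.** The point turns on comparing the two lists. The one figure nearby, the sample size, is checked first to see whether it is involved.

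**Sample size.** Section VI gives 126 patients in total, 80% power, effect size 0.5 and alpha 0.05. Assuming a two-sided test and equal arms (sidedness is not stated), the normal approximation gives

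n per arm = 2 × (1.960 + 0.842)² / 0.5² = 2 × 7.851 / 0.25 = 62.8, rounded up to 63; total 2 × 63 = 126.

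The plan's figure is reproduced. It is tied to the primary outcome, and EQ-5D does not enter it.

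**Schedule, from the two lists in Section V.**

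| Instrument | Enrollment | 1 week-1 month | 6 months |
|---|---|---|---|
| Quick-DASH | yes | yes | yes |
| EQ-5D | yes | no | no |
| PROMIS Upper Extremity CAT | no | yes | yes |
| Decision Conflict Scale | yes | yes | yes |
| Satisfaction scales | yes | yes | yes |
| Decision Regret scale | no | yes | yes |

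EQ-5D has one enrollment assessment and 0 of 2 at follow-up. If 1 week and 1 month are separate contacts, it is 0 of 3.

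**Is the follow-up list shorthand for repeating everything?** No. Quick-DASH, the Decision Conflict Scale and satisfaction are written out again although they are already in the enrollment list. Repeated instruments are therefore named, and EQ-5D is not.

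**Does the enrollment reading precede treatment?** Almost certainly. Section III excludes patients with earlier surgery or corticosteroid injection for the condition on the same limb, consent is taken at the baseline diagnostic assessment, and the visit with the physician resumes after the study procedures. The exact place of EQ-5D within the visit is not documented. The sentence about completing questionnaires after randomization refers to those on decisional conflict, and EQ-5D may instead belong to the baseline data.

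**Which planned analyses remain possible for EQ-5D?**
- Between arms at follow-up: none, because there are no data.
- Paired comparison across occasions: none, because there is one occasion and two are needed.
- Descriptive summary at each time point: enrollment only.
- Between arms at enrollment: possible, but before treatment could have acted.

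**What remains for the clinical-outcome aim?** Quick-DASH can be compared between arms at follow-up and within arms over time. PROMIS Upper Extremity can be compared between arms at follow-up. Both address upper-limb function.

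**The case against.** The best defence is that EQ-5D was meant as a baseline descriptor or covariate, for which one enrollment reading is enough, and that only the label is wrong. Headings in Section V are loose: the follow-up list places Quick-DASH and PROMIS under a heading about the decision-making process. The omission may also be clerical. All of this is possible, but the protocol gives EQ-5D no descriptive or covariate role and does call it a health outcome. Either the schedule or the label has to change.

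It is also fair to say that the consequence is limited. The primary hypothesis concerns decisional conflict. Clinical outcome is a secondary aim, Section II does not require a generic measure for it, and limb-specific function is a reasonable outcome in hand surgery. That part of the objection stands, and it bounds the point.

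Four stronger readings are tempting, and the documents do not support them.
- A reader might infer that the enrollment EQ-5D contrast must be zero whatever the aid does. The reading may follow randomization and use of the aid, and Section I reports that users of decision aids were less anxious, so a short-term shift in self-reported health is not excluded. Only an effect through treatment is ruled out.
- A reader might infer that the clinical-outcome aim cannot be tested. It can, on Quick-DASH and PROMIS.
- A reader might see the missing enrollment PROMIS as a matching defect. In a randomized comparison, a follow-up-only measure supports a valid contrast between arms; a baseline value would add precision but is not required.
- A reader might expect a null enrollment result to be presented as no effect on health. Nothing in the protocol plans such a report.

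**Conclusion.** The point holds for EQ-5D alone. One of the two instruments named as primary health outcomes has no follow-up assessment, so it cannot capture a treatment-mediated effect of the aid on generic health status, and two of the planned kinds of analysis (follow-up contrast and paired change) are unavailable for it. No numerical bias is claimed.

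This rests on two assumptions: that the follow-up list is complete as written, and that the enrollment visit precedes the chosen treatment. The text supports both, the second by inference. The word primary in the sub-heading should not be taken to mean the trial's primary endpoint. The gap is modest in consequence but worth an amendment, because it affects what the trial can say about a named outcome.

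**What to change.** Add EQ-5D to the follow-up list in Section V, at minimum at 6 months. State in Section VI that the arms are compared on it there, with the enrollment value available as a covariate. Because that value may currently be recorded after exposure to the aid, also state when in the enrollment visit EQ-5D is answered; a covariate is cleanest if taken before the aid is handed over.

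The cost is a protocol amendment and one short questionnaire in an online REDCap survey that is already sent, with slightly longer completion time. The sample size need not change.

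If EQ-5D is not added at follow-up, move it out of the primary health outcomes, describe it as a descriptive enrollment variable, and draw no conclusion about health outcome from it. That costs only a change of wording, but leaves the trial without any post-treatment measure of generic health.

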Based on previous studies, scores of 25 or lower on the DCS (0-100) are associated with low decisional conflict and following-through with decisions.¹⁵ On the other hand, scores of 39 or higher are associated with heightened mental conflict resulting in a delay in the decision making.¹⁵ Our study will measure the rate of patients having a conflict in decision-making. A sample size of 126 total patients was chosen to measure our primary outcome with 80% power, 0.5 effect size and an alpha of 0.05. Chi-square tests will be conducted to determine the differences between two categorical variables. Independent Student's t-tests will be performed to determine the differences between continuous and dichotomous variables. Paired samples T-test will be used to compare the mean scores for the same group on different occasions. Pearson's correlation or Spearman correlation will be used to explore the strength of the relationship between the conflict of decision-making and the use of decision aids. Wherever the minimum expected cell frequency is less than five, the Fisher's exact test will be used instead of the Pearson's Chi-square test. All variables with significant ($p < 0.05$) or near significant ($p < 0.08$) relationships will be evaluated with backwards multivariate/binary logistic regression (depending on the outcome variable) Descriptive statistics will be summarized in terms of means, standard deviations or frequencies, and will be calculated at each time point. Incomplete data will be adequately described and mean imputation will be used when deemed necessary. We will use IBM SPSS ® (19) to perform the data analysis.

VII. RISKS AND DISCOMFORTS (Stratify by common and uncommon)

The greatest discomfort associated with participation is the time required to fill out the decision aid and complete the questionnaires. Completing the DA will require approximately 20

minutes, but this can be done at home. The Questionnaires will require approximately 20 minutes at the time of enrollment.

VIII. POTENTIAL BENEFITS

Individuals managed without a DA will not experience any additional benefits, but will also not have any extra risks. Patients managed with a DA, on the other hand, may experience less decisional conflict and improved knowledge about their disease. The study will benefit society as a whole by providing a better understanding of the factors that influence patient decision-making and surgical outcomes for orthopedic problems.

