The principal investigator will be responsible for insuring that any adverse events are reported to the IRB or federal agencies as necessary. Adverse events will be reported to the IRB as soon as they are discovered by any study staff member and discussed with the PI or designee (within 24 hours). The research coordinator, supervised by the principal investigator will be responsible for cataloguing and tallying adverse events. Serious adverse events (SAEs) will be reported to the MGH IRB within 24 hours of their detection using the necessary written forms provided by the MGH IRB. All proposed staff have participated in the NIH required trainings in participation and conduct of studies that involve human subjects, and any future study staff will do so upon hiring. If any study staff discovers any untreated condition (e.g. onset of substance abuse or physical condition), they will refer participants to appropriate treatment immediately. Study staff will follow Massachusetts's laws regarding mandated reporting for psychologists (i.e. discovery of abuse to a child, elder, or disabled person, participant is imminent danger of hurting themselves or an identifiable other person).

All participants are given a participation number/code at the time of enrollment. This code is kept on all data sheets instead of the patient name. Subject information is only accessible by Partners authorized investigators and will not be shared with outside entities. The final results after statistical analysis will not be shared with any other institution.

Study data will be collected and managed electronically using REDCap, a free online research management tool. It enables researchers to create study-specific websites for capturing participant data securely. The National Institutes of Health funded Patient Reported Outcomes Measurement Information System (PROMIS) questionnaires use IRT and CAT technology, which makes completing questionnaires less burdensome for patients. This technique uses fewer questions to get the same information on patient-reported health status, since it selects the

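### 6-month PROMIS Upper Extremity has no enrollment score and is compared by an unadjusted t-test; adjusting for enrollment Quick-DASH and diagnosis would gain precision at no data cost

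*Combined protocol and SAP*

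**What the plan says.** Section V lists Quick-DASH and EQ-5D at enrollment under "Primary health outcomes variables". PROMIS is not in that list. The follow-up list, for 1 week to 1 month and for 6 months, contains Quick-DASH and "PROMIS Upper Extremity CAT" but not EQ-5D. Of the health measures, only Quick-DASH is therefore scheduled on both occasions.

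Section III recruits across five conditions: adults "with moderate or severe TMC arthrosis, CTS, CTD, DRF and TF will be invited to enroll". Section IV assigns them "with a computer generated simple randomization sequence". Section II speaks of two cohorts for each diagnosis, but Section IV mentions no stratification.

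Section VI compares the arms on continuous variables with independent t-tests. It adds "Paired samples T-test will be used to compare the mean scores for the same group on different occasions". It names no enrollment score and no diagnosis term as a prespecified covariate for any outcome. Its only regression is backward selection among variables that pass a p-value screen.

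Clinical outcome is part of the secondary null hypotheses in Section II, which do not name an instrument.

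**The concern.** Two upper-limb function scales are treated differently, and no reason is given. Without an enrollment value, PROMIS cannot be expressed as change from enrollment and balance on it cannot be shown. The paired test can only compare the first follow-up with 6 months. The first follow-up comes after randomization, within a window of 1 week to 1 month, so it cannot stand in for a baseline.

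What is at stake is precision. A fracture, a trigger finger, two nerve compressions and thumb arthrosis are likely to start at different levels of function. Whatever part of that spread persists to 6 months enters the error term of an unadjusted comparison. Simple randomization may also leave the arms unequal in case mix or starting function by chance, and the planned test makes no allowance for that.

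**Working it through.** **Inputs.** From Section VI: "A sample size of 126 total patients was chosen to measure our primary outcome", with "80% power, 0.5 effect size and an alpha of 0.05". The allocation ratio and sidedness are not stated; 1:1 and two-sided are assumed. The documents give no correlation between any enrollment score and 6-month PROMIS, so every correlation below is an assumption, shown as a range.

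**1. The plan's figure.** n per arm = 2(1.960 + 0.842)²/0.5² = 62.8, rounded up to 63, or 126 in total. The stated size reproduces. A t-distribution calculation gives 128 (power 79.5% at 63 per arm); a one-sided test gives 100. The 126 was set for the primary outcome, not for PROMIS.

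**2. Adjusted against unadjusted.** In SD units, the standard error of the unadjusted arm difference is √(2/63) = 0.178. With a pre-randomization covariate correlated r with the 6-month score, it is multiplied by √(1 − r²). Power is by normal approximation at the plan's effect size of 0.5, with all 126 analysed; equivalent N is 126/(1 − r²).

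| r | SE factor | SE reduction | Power | Equivalent N |
|---|---|---|---|---|
| 0 (planned t-test) | 1.000 | 0% | 80.1% | 126 |
| 0.3 | 0.954 | 4.6% | 83.7% | 138 |
| 0.4 | 0.917 | 8.3% | 86.5% | 150 |
| 0.5 | 0.866 | 13.4% | 90.0% | 168 |
| 0.6 | 0.800 | 20.0% | 93.9% | 197 |

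Loss to follow-up lowers the power column but leaves the SE factor unchanged.

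**3. A PROMIS baseline without a change of analysis.** The planned t-test does not use an enrollment score, so collecting one changes the precision of the 6-month comparison by 0%. A t-test on change scores has variance 2(1 − r) times that of the 6-month score: 1.4 at r = 0.3, 1.0 at r = 0.5, 0.8 at r = 0.6. It helps only when r exceeds 0.5.

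**4. What a PROMIS baseline adds beyond Quick-DASH.** Let q and p be the correlations of enrollment Quick-DASH and enrollment PROMIS with 6-month PROMIS, and c the correlation between the two enrollment scores. With both in the model, R² = (q² + p² − 2qpc)/(1 − c²). The further SE factor is √[(1 − R²)/(1 − q²)].

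| q | p | c | R², Quick-DASH only | R², both | Further SE reduction |
|---|---|---|---|---|---|
| 0.5 | 0.5 | 0.8 | 0.250 | 0.278 | 1.9% |
| 0.4 | 0.5 | 0.7 | 0.160 | 0.255 | 5.8% |
| 0.4 | 0.6 | 0.7 | 0.160 | 0.361 | 12.8% |
| 0.3 | 0.6 | 0.7 | 0.090 | 0.388 | 18.0% |

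**5. Cost of fitting the covariates.** Quick-DASH plus four diagnosis indicators makes five terms, so residual degrees of freedom fall from 124 to 119. Estimating them inflates the standard error by about √(1 + 5/118) = 1.021, or 2%, offset by whatever diagnosis itself explains.

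**6. Chance imbalance.** The difference between arms in mean starting function also has a standard error of 0.178 SD, so differences up to 1.96 × 0.178 = 0.35 SD are ordinary chance. On PROMIS such a difference could not be seen. Through Quick-DASH it could be seen and partly allowed for.

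**The case against.** The strongest reply is that the missing baseline is not what costs precision. Quick-DASH has an enrollment score and would get the same unadjusted test. That stands, and it is why the remedy below starts with the analysis and not with the questionnaire.

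A reader might infer that PROMIS cannot be adjusted for starting function at all. The documents do not support this. Enrollment Quick-DASH measures upper-limb function, and diagnosis is confirmed by the study physician at recruitment (Section III). Only adjustment on the same scale is lost.

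A reader might also infer that the missing baseline biases the comparison or leaves the clinical-outcome hypothesis untestable. Neither follows. Randomization protects the 6-month comparison, and Quick-DASH is measured on both occasions.

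It is also fair to say that the gain rests on an unknown correlation. Mixing an acute fracture with chronic conditions may push it toward the low end, where the benefit is small. One further point stands: Section V says baseline data are gathered at enrollment, but also places the decision-conflict questionnaires after randomization. It does not say on which side of randomization Quick-DASH falls, so its use as a covariate depends on settling that.

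**Conclusion.** The point holds as a matter of precision. PROMIS has no enrollment value, its paired test is confined to the two follow-ups, and the planned arm comparison is unbiased but less precise than data already scheduled would allow. Against no adjustment, the standard error would fall by about 5 to 20% for assumed correlations of 0.3 to 0.6, before a fitting cost of about 2%. An enrollment PROMIS score would take off roughly a further 2 to 18% beyond Quick-DASH, depending on the three correlations assumed. These figures take 1:1 allocation and a covariate measured before randomization.

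It is tempting to charge the whole 5 to 20% to the missing PROMIS baseline. That is not supported: under the planned t-test the baseline alone gains nothing, and Quick-DASH can recover part of the precision. The matter concerns a secondary clinical measure and does not touch decisional conflict, the primary hypothesis, or the validity of the trial.

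**What to change.** In Section VI, replace the t-test for 6-month PROMIS with a prespecified linear model: 6-month score on arm, enrollment Quick-DASH and diagnosis (five categories). Report the adjusted arm difference with its 95% confidence interval. Analyse 6-month Quick-DASH with the same model. In Section V, state that enrollment Quick-DASH is completed before randomization. The cost is a few lines of text and, if Quick-DASH currently follows randomization, moving it ahead. No new data are needed.

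Optional: give the PROMIS CAT at enrollment, before randomization, and include it as a covariate. The downside is added burden on a battery that Section V puts at about 20 minutes. The documents give no completion time for the CAT, but Section IX says of it that "This technique uses fewer questions to get the same information on patient-reported health status". An enrollment score that is not taken cannot be recovered later, so this choice has to be made before recruitment.
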